4. STATISTICAL ANALYSES

4.1. General Considerations

4.1.1. General Methodology

Participants who withdraw from the study may be replaced, with any replacements beginning from the start of the study.

Summary tables will provide the following descriptive statistics as a minimum, unless otherwise specified:

- Continuous data (normally distributed):
n, mean, standard deviation (SD), median, minimum and maximum.
- Continuous data (log-normally distributed):
n, geometric mean, SD on the log scale (SD (log)), median, minimum and maximum.
- Categorical data:
number and percentage of participants in each category.

4.1.2. Baseline Definition

For all endpoints the baseline value will be the latest pre-dose assessment with a non-missing value, including those from unscheduled visits. If time is not collected, Day 1 assessments are assumed to be taken prior to first dose and used as baseline.

The CCL17 levels (free, total) baseline value will be derived by averaging the two pre-dose measurements (Day -2 and Day 1 pre-dose).

Unless otherwise stated, if baseline data is missing no derivation will be performed and baseline will be set to missing.

4.2. Primary Endpoints Analyses

The primary endpoints for this study are:

- Incidence of AEs, SAEs, withdrawals due to AEs
- Occurrence of clinically important changes from baseline in clinical laboratory parameters (haematology, clinical chemistry, urinalysis), vital signs (blood pressure, heart rate, body temperature), and cardiac parameters (electrocardiogram)
- PK parameters: area under the concentration-time curve (AUC(0-56), AUC(0-t)), time of occurrence of last quantifiable concentration (tlast), maximum observed

concentration (Cmax), and time of occurrence of Cmax (tmax) per cohort as data permits

4.2.1. Pharmacokinetics

All PK analyses will be performed on the PK population. Serum GSK3858279 concentration-time data will be analysed by non-compartmental and/or model-based methods, as appropriate. Calculations will be based on the actual sampling times recorded during the study. Concentration-time data will be listed for each participant and summarized by planned time point and cohort. The following summary statistics will be calculated for each cohort:

- Geometric mean, 95% CI of the geometric mean, SD(log), median, min and max

Individual serum concentration-time data and summary data will be graphically displayed.

From the serum concentration-time data collected up to Day 57, the following PK parameters will be determined, as data permit:

- Area under the serum concentration-time curve (AUC(0-56), AUC(0-t))
- Time of last quantifiable concentration (tlast)
- Maximum observed concentration (Cmax)
- Time of occurrence of Cmax (tmax)

4.2.1.1. Summary Measures of Derived Parameters

PK parameters will be listed for each participant and summarized descriptively by cohort. For each of these parameters, except for tmax and tlast, the following summary statistics will be calculated for each cohort:

- Median, maximum, minimum, arithmetic mean and standard deviation of non-transformed data.
- Geometric mean, 95% confidence interval (CI) for the geometric mean, standard deviation and coefficient of variation of logarithmically transformed data.

For tmax and tlast, arithmetic mean, standard deviation, median, maximum and minimum will be calculated.

4.2.1.2. Statistical Analysis

Table 1 Statistical Analysis of Primary Endpoint(s)

Endpoint

 • AUC(0-56) • Cmax
Model Specification

 • The PK parameters will be \log_e transformed and analysed using a mixed model. • Terms fitted in the model will include ethnicity and $\log_e(\text{body weight})$. • An additional model including the ethnicity term only will be fitted.
Model Checking & Diagnostics

 • Normality assumptions underlying the model used for analysis will be examined by obtaining a normal probability plot of the residuals and a plot of the residuals versus the fitted values (i.e. checking the normality assumption and constant variance assumption of the model, respectively) to gain confidence that the model assumptions are reasonable. • If there are any departures from the distributional assumptions, alternative models will be explored using appropriate transformed data.
Model Results Presentation

 • Geometric mean and 90% CIs will be calculated for each of the ethnic cohorts. • Comparisons for Japanese/Caucasians and Chinese/Caucasians will also be presented – this will be determined as differences on the \log_e scale back transformed to present as ratios.

4.2.2. Safety

The following primary safety endpoints will be summarised descriptively by ethnic cohort and treatment group, as described in Section 4.5:

- Incidence of adverse events (AEs)
- Serious adverse events (SAEs)
- Withdrawals due to AEs

- Occurrence of clinically important changes from baseline in clinical laboratory parameters, vital signs and ECGs

4.2.3. Sensitivity analyses

No formal sensitivity analyses are planned.

4.3. Secondary Endpoint(s) Analyses

The secondary endpoints for this study are:

- Reduction (%) from baseline in free CCL17: maximum, minimum and at Days 7, 14, 28 and 56 post-dose
- Total CCL17 (free and when bound to GSK3858279): maximum observed concentration (Cmax), time of Cmax (tmax), maximum fold increase compared to baseline, fold increase compared to baseline at Days 7, 14, 28 and 56 post-dose.
- Incidence of pre-existing ADAs
- Incidence of treatment-emergent ADAs over time (and whether neutralising)

4.3.1. Target Engagement

All TE analyses will be performed on the TE population. Calculations will be based on the actual sampling times recorded during the study.

Free and total CCL17 concentration-time data will be listed for each participant and summarized by planned time point and cohort.

For Free CCL17, Total CCL17 and Total CCL17 Fold Increase parameters, the following summary statistics will be calculated for each cohort:

- Geometric mean, 95% CI of the geometric mean, SD(log), median, min, and max

For Free CCL17 Percentage Reduction parameter, the following summary statistics will be calculated for each cohort:

- Geometric mean, 95% CI of the geometric mean, SD(logit), median, min, and max

Individual serum concentration-time data and summary data will be graphically displayed.

From the serum concentration-time data collected up to Day 57, the following target engagement parameters will be derived, as data permit:

- Baseline for free and total CCL17
- Percentage reduction from baseline in free CCL17 by time point (Days 7, 14, 28 and 56 post-dose)
- Minimum and maximum percentage reduction from baseline in free CCL17
- Cmax and tmax for total CCL17
- Fold increase compared to baseline for total CCL17 by time point
- Maximum fold increase compared to baseline for total CCL17

4.3.1.1. Summary Measures of Derived Parameters

TE parameters will be listed for each participant and summarized descriptively by cohort. For each of these parameters, the following summary statistics will be calculated for each cohort:

- Median, maximum, minimum, arithmetic mean and standard deviation of non-transformed data.
- Geometric mean, 95% CI for the geometric mean, standard deviation and coefficient of variation of logarithmically transformed data.
- Geometric mean, 95% CI for the geometric mean and standard deviation of logit transformed data. A logit-transformation will be used for the percentage reduction (including minimum and maximum) parameter.

For tmax, arithmetic mean, standard deviation, median, maximum and minimum will be calculated.

[figure not shown]

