3. ANALYSIS SETS

Analysis Set	Definition / Criteria	Analyses Evaluated
Screened	All participants who were screened for eligibility.	Study Population
Enrolled	
All participants who entered the study, signed the ICF and were eligible for randomisation (regardless of whether the participant went on to be randomised).
 
Note screening failures (who never passed screening even if rescreened) and participants screened but never enrolled into the study (met eligibility but not needed) are excluded from the Enrolled analysis set as they did not enter the study.
	Study Population
Randomised	
All participants who were randomly assigned to study intervention in the study.
 
Data will be reported according to the randomised study intervention.
	Study Population
Safety	
All participants who received at least one injection of study intervention.
 
Data will be reported according to the actual study intervention received.
	Safety
Pharmacokinetic (PK)	
All participants in the safety population who received an active dose of study treatment and had at least one reportable PK assessment (Non-quantifiable [NQ] values will be considered as reportable values).
 
Participants will be analysed according to the study intervention they actually received.
	PK
Target Engagement (TE)	
All participants in the safety population who had at least one reportable TE assessment (Non-quantifiable [NQ] values will be considered as reportable values).
 
Participants will be analysed according to the study intervention they actually received.
	TE

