4.7.2. Other

Prior to the primary PK and TE analysis, an additional interim analysis including Study Population, Safety, TE and PK data may be performed to support regulatory submissions. The data will be assessed in an unblinded manner. No changes to the conduct of the study will be implemented as a result of the interim analyses.

This interim analysis will occur on all available data at a specified timepoint. This timepoint will be decided by the central study team in conjunction with the Chinese and Japanese LOCs.

As the primary purpose of the interim analyses is to provide Safety and PK data to regulators – to support China and Japan’s potential participation in GSK3858279’s phase 2 programs – data at both an individual and aggregate treatment group level will be provided.

The full list of outputs being produced by the GSK Biostatistics Team (including Third Party Suppliers) for inclusion in this interim analysis are detailed in the OPS. GSK CPMS Team (including Third Party Suppliers) will produce additional outputs as appropriate.

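### The logit summary planned for percentage reduction in free CCL17 cannot be computed for reductions at or below 0%, which placebo participants will often have, and no visible rule covers this

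*SAP*

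**What the plan says.** The first secondary endpoint (SAP 1.1 and 4.3) is percentage reduction from baseline in free CCL17: maximum, minimum, and at Days 7, 14, 28 and 56. SAP 4.3.1 lists its statistics as "Geometric mean, 95% CI of the geometric mean, SD(logit), median, min, and max". SAP 4.3.1.1 repeats the geometric mean, 95% CI and SD on the logit scale and adds: "A logit-transformation will be used for the percentage reduction (including minimum and maximum) parameter".

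Other text that bears on the point:

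- **Who is included.** SAP 3 defines the TE set as "All participants in the safety population who had at least one reportable TE assessment". The PK set in the same table requires an active dose; the TE set does not. Allocation is 7 active to 3 placebo per cohort (SAP 5).
- **Baseline.** SAP 4.1.2 uses the average of the Day -2 and Day 1 pre-dose values.
- **Other summaries.** SAP 4.3.1.1 also gives "Median, maximum, minimum, arithmetic mean and standard deviation of non-transformed data", and participant listings. Free CCL17 concentration, total CCL17 and total CCL17 fold increase get "Geometric mean, 95% CI of the geometric mean, SD(log), median, min, and max" (SAP 4.3.1).
- **Layout.** "TE parameters will be listed for each participant and summarized descriptively by cohort"; treatment group is not named in that sentence.
- **Qualifier.** SAP 4.3.1 says the TE parameters will be derived where the data allow. No truncation, offset, exclusion or active-only rule is visible.

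**The concern.** A percentage reduction is zero or negative whenever the post-dose value equals or exceeds baseline. In an untreated participant that should happen at close to half of all visits, and at one visit or more for most participants. The minimum reduction, which the SAP assigns to the logit by name, is each participant's worst value and so is the most exposed. The stated statistic therefore fails on data that can be foreseen.

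At stake is the placebo reference for this endpoint. With no rule, whoever programs the table must choose between dropping, truncating, offsetting and reporting not calculable, possibly after unblinding. Those choices give different placebo results.

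**Working it through.** The documents give no figure to reproduce, so the check is the domain of the transformation followed by how often placebo values fall outside it.

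**Domain.** With p the reduction as a proportion, logit(p) = ln(p/(1-p)). At p = 0.90 it is 2.197 and at p = 0.05 it is -2.944. At p = -0.10, 0 and 1.00 it is undefined. The log-transformed summary in the same list does not rescue this, because ln(p) is also undefined for p at or below 0.

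**Inputs from the documents.** The baseline is a two-sample mean and there are 3 placebo participants per cohort. The visible schedule has TE samples at 6, 12, 24, 36 and 48 h and on Days 5, 8, 15, 22 and 29, which is 10 post-dose samples.

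**Assumptions, not in the documents.** Day 57 is added to make 11 samples. Samples are log-normal with within-person log-SD 0.1 to 0.5 and no drift on placebo. The correlation among post-dose samples is 0 to 0.8.

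**How often a placebo value is undefined.** The reduction is 1 - X/B, where X is the post-dose value and B the mean of the two pre-dose values. By simulation, the probability of a value at or below 0% is:

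| Within-person log-SD | 0.1 | 0.2 | 0.3 | 0.5 |
|---|---|---|---|---|
| Single day | 0.49 | 0.48 | 0.48 | 0.46 |
| Minimum, correlation 0 | 0.96 | 0.96 | 0.95 | 0.95 |
| Minimum, correlation 0.8 | 0.72 | 0.71 | 0.71 | 0.69 |
| Maximum, correlation 0 | 0.04 | 0.03 | 0.03 | 0.03 |
| Maximum, correlation 0.8 | 0.27 | 0.26 | 0.25 | 0.24 |

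Correlation matters for the minimum and maximum because five of the 11 samples fall within 48 hours. It hardly affects a single day.

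**Per cohort-day.** Let q be the single-day probability. The chance that at least one of 3 placebo values is undefined is 1 - (1-q)^3:

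- q = 0.491 gives 1 - 0.509^3 = 0.868.
- q = 0.463 gives 1 - 0.537^3 = 0.845.

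**If undefined values were dropped** (one possible handling). Fewer than 2 of 3 values remain, so no SD or CI exists, with probability q^3 + 3q^2(1-q):

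- q = 0.491 gives 0.118 + 0.368 = 0.486.
- q = 0.463 gives 0.099 + 0.345 = 0.445.

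The logit mean of the surviving placebo values is a reduction of 6.4%, 12.8%, 19.1% and 31.2% across the four log-SDs. The true median reductions are 0.3%, 1.0%, 2.1% and 5.6%; they are not exactly zero because an arithmetic-mean baseline of skewed values sits slightly high. The log-ratio estimate on all values lies within about 0.2 percentage points of the true median.

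**Worked illustration.** Take three invented placebo reductions of +20%, +5% and -15%.

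- *Logit with the negative value dropped (n = 2).* The logits are -1.386 and -2.944, with mean -2.165 and SD 1.102. The half-width is 12.706 x 1.102/sqrt(2) = 9.90. Back-transformed, this is 10.3% (95% CI 0.0006% to 99.96%).
- *Log-ratio on all three.* ln(0.80), ln(0.95) and ln(1.15) are -0.223, -0.051 and 0.140, with mean -0.0449 and SD 0.1815. The half-width is 4.303 x 0.1815/sqrt(3) = 0.451. The reduction is 1 - exp(-0.0449) = 4.4% (95% CI -50% to 39%).

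**Active participants.** Under independent samples, the probability of an undefined single-day value is 0-2% at a true 70% reduction, 0-11% at 50% and 0-25% at 30%.

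**The case against.** **Little depends on it.** No hypotheses are tested, the endpoint is descriptive, and the median, range, arithmetic mean, SD and listings remain defined for negative reductions. With 3 placebo participants no 95% CI says much; the log-ratio interval above runs from -50% to 39%. This stands, and it is why the point is minor.

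**A rule may exist elsewhere.** The output specification that SAP 4.7 refers to and the project data analysis plan in SAP 7 were not available, and some SAP text is redacted. This stands too: the claim is only that no rule is visible. The qualifier that parameters are derived where data allow does not supply one. A reduction of -10% can be derived; only its logit cannot.

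**The logit suits strongly suppressed active values.** It does, and replacing it for the active arm is partly preference. The Protocol synopsis reports incomplete return of free CCL17 to baseline in Part A of the earlier study, which limits undefined active values.

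A reader might infer three stronger things that the documents do not support:

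- *That the placebo arm will show a spurious reduction.* That follows only if undefined values are dropped. The SAP does not say they will be, and reporting not calculable would create no such bias.
- *That active and placebo are pooled.* The TE set says "Participants will be analysed according to the study intervention they actually received", which makes separate arms the natural reading. SAP 4.7.2 says "data at both an individual and aggregate treatment group level will be provided", but it gives safety and PK as the purpose and does not settle TE table layout. The wording is incomplete; it does not show pooling. If arms were pooled, the undefined placebo values would enter the pooled statistic.
- *That the target engagement results or the PK comparison are unsound.* Log-scale free CCL17 concentrations and the primary PK analysis do not use the logit.

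**Conclusion.** The point holds as a minor one. The logit mean, 95% CI and SD are prescribed for a population in which they cannot be computed for a large share of placebo values, and no visible text restricts the transformation or handles the exceptions.

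That the logit fails at or below 0% and at 100% is certain. The frequencies, about 46-49% on a single day, 69-96% for the minimum and 3-27% for the maximum, rest on the assumed log-normal variation, no drift and 11 samples. Drift matters: a shift of 10% in either direction moves the single-day figure to 19-78% under independent samples, so the problem persists but its size is not fixed by the documents. The 44-49% of cohort-days with fewer than 2 of 3 values, and the 6-31% apparent placebo reduction against a true median of 0-6%, depend further on dropping undefined values. No primary result or error rate is affected.

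**What to change.** In SAP 4.3.1 and 4.3.1.1:

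1. For the placebo group at least, and preferably for both arms so that they share one scale, summarise log_e(post-dose/baseline) for free CCL17. Report 100 x (1 - geometric mean ratio) with its 95% CI, allowing negative values. This is the scale already used for total CCL17 fold increase.
2. Use median and range for the minimum and maximum reduction.
3. If the logit is kept for active participants, state that it applies to active only, report the number of values at or below 0% or at 100%, and do not calculate the logit statistic for a group containing such values.
4. State that TE summaries are by cohort and treatment group.
5. State one positive value to substitute for non-quantifiable free CCL17 results. A zero would give a 100% reduction on the logit scale and an undefined log-ratio.

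Keep the planned untransformed summaries and listings. The cost is a few lines of SAP text and a simple derivation, with no new samples or data. The downside is that percentage-scale intervals can fall below 0% or, if the logit is kept for active participants, that two scales are reported.

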4.3.2. Anti-drug antibody (ADA) formation

The incidence of pre-existing ADAs and the incidence of treatment-emergent ADAs over time (and whether neutralising) will be summarised descriptively.

[figure not shown]
4.3.3. Sensitivity analyses

No formal sensitivity analyses are planned.

[figure not shown]
4.4. Exploratory Endpoint Analyses

[figure not shown]
CCI

CCI

CCI

4.5. Safety Analyses

The safety analyses will be based on the Safety Analysis Set, unless otherwise specified.

Safety data will be presented by ethnic cohort and treatment group.

4.5.1. Adverse Events

An adverse event (AE) is considered study intervention emergent if the AE onset date is on or after study intervention start date. All AE summaries will be based on study intervention emergent events unless otherwise specified. SAE summaries will be based on all SAEs reported regardless of whether they meet the definition of study intervention emergent or not. All AE and SAE summaries will be by preferred term (PT) and System Organ Class (SOC).

Adverse events will be coded using the standard Medical Dictionary for Regulatory Affairs (MedDRA dictionary).

An overview summary of AEs, including counts and percentages of participants with any AE, AEs related to study intervention, mild, moderate, or severe AEs, SAEs, SAEs related to study intervention, fatal SAEs, and fatal SAEs related to study intervention will be produced.

A separate summary will be provided for study intervention-related AEs. A study intervention-related AE is defined as an AE for which the investigator classifies the possible relationship to study intervention as “Yes”. A worst-case scenario approach will be taken to handle missing relatedness data, i.e. the summary table will include events with the relationship to study intervention as ‘Yes’ or missing.

All SAEs will be tabulated based on the number and percentage of participants who experienced the event. Separate summaries will also be provided for study intervention-related SAEs.

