4.5.2. Additional Safety Assessments

4.5.2.1. Laboratory Data

Summaries of worst-case changes from baseline with respect to Potential Clinical Importance (PCI) Criteria will be generated. Decreases to low, changes to normal or no changes from baseline, and increases to high will be summarized for the worst-case post-baseline. If a subject has a decrease to low and an increase to high during the same time interval, then the subject is counted in both the “Decrease to Low” categories and the “Increase to High” categories.

Separate summary tables for haematology, and chemistry laboratory tests will be produced. Liver function laboratory tests will be included with chemistry lab tests.

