4.5.2.2. Vital Signs

A summary of change from baseline vital sign values will be provided by visit and treatment group, including systolic blood pressure, diastolic blood pressure, heart rate and temperature.

Summaries of vital sign results relative to PCI criteria will also be provided. The summary will include baseline, planned visit and worst-case post baseline.

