4.5.2.3. ECG

The baseline ECG will be taken as the mean of the triplicate values collected pre-dose on Day 1. The following will be summarised by visit: ECG findings and change from baseline in ECG values.

The number of subjects with maximum QTc values at baseline and post-baseline relative to baseline will be summarized using the following categories: No Change or Decrease To ≤ 450 , Any Increase > 450 , Increase To > 450 to ≤ 480 , Increase To > 480 to ≤ 500 , and Increase To > 500 .

The changes in QTc values will be categorized into the clinical concern ranges which are specific to changes in QTc: Increase of ≤ 30 , 31-60 and > 60 msec. A summary of change in QTc value will display the number and percentage of subjects with a change within each range for the worst-case post-baseline only. Subjects with missing baseline values will be excluded from this summary.

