6.2.2. Study Phase

Assessments and events will be classified according to the time of occurrence relative to the study intervention period.

Pre-Intervention is defined as time prior to the single dose of study intervention.

On-Intervention is defined as time following single dose. If time of assessment (e.g. ECG, Lab, vital signs) is not collected and assessment date is the same as the dose date, the assessment is considered pre-intervention. If time of study intervention (e.g. AE, concomitant medication) is not collected and the start/end date is the same as dose date, it is considered on-intervention.

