6.2.4. Assessment Window

For data summaries by visit, scheduled visits with nominal visit description as well as the worst-case post baseline will be displayed. Unscheduled visits will not be displayed or slotted into a visit window but will be included in the derivation of worst-case post baseline assessment. All unscheduled visits will be displayed in the listing.

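### By-cohort safety tables in SAP 4.5 have no closing day, although late follow-up is mandatory for Caucasian participants and optional for Chinese and Japanese participants

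*SAP*

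**What the plan says.** **Display.** SAP 4.5: "Safety data will be presented by ethnic cohort and treatment group".

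**Safety windows.** SAP 4.5.1 sets only a start for AEs: "An adverse event (AE) is considered study intervention emergent if the AE onset date is on or after study intervention start date". SAE summaries take every SAE reported. SAP 6.2.2 leaves the phase open: "On-Intervention is defined as time following single dose". The other safety tables rest on extremes over the whole post-baseline period:
- Laboratory (SAP 4.5.2.1): "Summaries of worst-case changes from baseline with respect to Potential Clinical Importance (PCI) Criteria will be generated".
- Vital signs (SAP 4.5.2.2): "The summary will include baseline, planned visit and worst-case post baseline".
- QTc change (SAP 4.5.2.3): counted "within each range for the worst-case post-baseline only".
- Unscheduled visits (SAP 6.2.4) "will be included in the derivation of worst-case post baseline assessment".

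**PK and target engagement (TE).** Here a limit is stated. SAP 4.2.1: "From the serum concentration-time data collected up to Day 57, the following PK parameters will be determined, as data permit". SAP 4.3.1 does the same for TE parameters.

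**Follow-up.** Protocol 4.1 requires the Caucasian cohort to stay to a later visit. Chinese and Japanese participants have their own final required visit and may choose to stay on; a footnote to the schedule of activities marks visits as optional for them. The end days are redacted. Protocol 8.3.1 collects AEs from dosing to the follow-up visit.

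**Day 57.** Protocol 1.1 says that primary endpoints are defined from data up to and including Day 57 (the text just before this is redacted). Its next sentence says that safety information is collected throughout the study. SAP 4.2.2 sends the primary safety endpoints to Section 4.5 without saying whether the Day 57 limit applies to them. SAP 4.7.1 plans a safety analysis once all participants have completed Day 57, run as in Section 4.5, with its outputs listed in the OPS.

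**The concern.** The proportion of participants with at least one AE, or with a worst value beyond a threshold, can only rise as observation lengthens. If one cohort is watched longer by design, its cumulative percentages tend to be higher even when the underlying risk is the same.

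Protocol 1.1 presents the study as a way to make inter-ethnic comparisons without cross-study variation, and as support for including Chinese and Japanese participants in later trials. Side-by-side cohort columns will be read in that light. A higher count in the Caucasian column could be taken for a cohort difference, or could make the Chinese and Japanese columns look reassuring, when only follow-up differs. The disposition summary in SAP 6.1.1 counts completers and withdrawals, and the SAP describes no display of follow-up duration by cohort that would alert the reader.

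What is at stake is a descriptive reading, not a formal inference.

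**Working it through.** **1. Is there a closing day anywhere?** SAP 4.5.1, 4.5.2, 6.2.2 and 6.2.4 give none. SAP 4.7.1 fixes when the Day 57 analysis is run (after the last participant reaches Day 57). It states no cut of each participant's data at his or her own Day 57, so participants dosed earlier may contribute later data.

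**2. Which tables are exposed?** AE and SAE incidence, the worst-case laboratory table, the worst-case column for vital signs, and the maximum and worst-case QTc tables. Vital-sign and ECG summaries by visit can be compared at shared visits. SAP 4.5.2.1 describes no by-visit laboratory summary.

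**3. How large could the effect be?** The plan gives no figure to reproduce, so this is an illustration.

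Assumed inputs:
- *p*, the AE incidence over 56 days after dosing: 10% to 50%, the same true risk in every cohort.
- Chinese and Japanese follow-up: 112 days (Day 113 appears in a protocol amendment row on COVID-19 testing). Alternative: 140 days (Day 141 appears in a row on visit windows).
- Caucasian follow-up: 154 days (Day 155, same row) to 196 days (the 28-week contraception period in protocol 5.1, which is not a visit).
- No visible text confirms any of these as an end day.
- *u*, the share of Chinese and Japanese participants who stay on: 0 to 1.
- 7 active participants per cohort (protocol 9.3).

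Formulas:
- Constant hazard: F(T) = 1 − (1 − p)^(T/56).
- Gap = (1 − u) × [F(Caucasian T) − F(Chinese/Japanese T)].
- Standard error (SE) = √[a(1 − a)/7 + c(1 − c)/7], where a and c are the two incidences.

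Example with p = 0.3 and u = 0: F(112) = 1 − 0.7^2 = 51.0%; F(196) = 1 − 0.7^3.5 = 71.3%; gap 20.3 points, or 1.4 of 7 participants; SE = √(0.510 × 0.490/7 + 0.713 × 0.287/7) = 25.5 points; ratio 0.80.

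Constant hazard, u = 0, Chinese/Japanese follow-up 112 days:

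| p | F(112) | F(154) | gap (SE) | F(196) | gap (SE) |
|---|---|---|---|---|---|
| 10% | 19.0% | 25.2% | 6.2 (22.1) | 30.8% | 11.8 (22.9) |
| 20% | 36.0% | 45.9% | 9.9 (26.2) | 54.2% | 18.2 (26.1) |
| 30% | 51.0% | 62.5% | 11.5 (26.3) | 71.3% | 20.3 (25.5) |
| 40% | 64.0% | 75.5% | 11.5 (24.4) | 83.3% | 19.3 (23.0) |
| 50% | 75.0% | 85.1% | 10.1 (21.2) | 91.2% | 16.2 (19.6) |

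The gap is 0.28 to 0.84 of one SE.

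Other assumptions:
- 140 versus 154 days, constant hazard, u = 0: 2.0 points at p = 10% (25.2 − 23.2), and at most 3.5 points over the range of p (at 30%: 62.5 − 59.0).
- Front-loaded AEs, with exponent (T/56)^0.5, 112 versus 154 to 196 days: 2.2 points (p = 10%, 154 days) to 10.2 points (p = 50%, 196 days).
- Half of the Chinese and Japanese participants stay on: every gap halves. All stay on, or all AEs fall by Day 57: zero.

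**4. After a common cut.** With every participant cut at 56 days after dosing, equal risk gives equal expected incidence. At p = 30% that is 0.3 × 7 = 2.1 of 7 in each cohort.

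Laboratory and QTc flags are not quantified, because the late visit schedule is redacted.

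**The case against.** The strongest reply is that the plan never makes the comparison at issue. The safety objective is active versus placebo, and within a cohort both arms follow one schedule. The Japanese/Caucasian and Chinese/Caucasian ratios are specified only for AUC(0-56) and Cmax, from data up to Day 57. No hypothesis is tested. This stands, and it is why the point is minor. It does not remove it, because the tables are still laid out by cohort.

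A second reply is that counting every collected event is a deliberate whole-study summary, since protocol 1.1 says safety information is collected throughout. That is reasonable, and the whole-study tables should stay. But when collection ends is a different question from what window makes cohorts comparable.

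A third is that the Day 57 analysis, whose data SAP 4.7.1 intends for regulators, already protects the main use. This is partly right. Individual data will be supplied, so timing may be visible, and protocol 1.1 aims to dose the groups concurrently. A reader might infer that this analysis is itself distorted. That would need one cohort to be dosed appreciably earlier than another, and the documents give no support for that.

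A reader might also infer that the SAP contradicts the protocol by not cutting safety at Day 57. The documents do not go that far: the text just before the Day 57 statement is redacted, and the sentence after it points to collection throughout. The SAP leaves open whether the limit covers safety.

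Finally, the OPS was not available and may list common-window tables.

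**Conclusion.** The point holds as a minor one. Followed as written, SAP 4.5 yields whole-study cohort percentages that mix cohort with observation time in the AE, SAE and worst-case tables. Within-cohort contrasts with placebo and by-visit summaries are largely unaffected.

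The size is unknown. The range of 0 to about 20 percentage points depends wholly on assumed end days, uptake, AE rates and hazard shape. The top of it needs no optional uptake, constant hazard after a single dose, and 112 versus 196 days. It should not be read as an estimate of bias, and throughout it stays below one SE of the difference between two cohorts of 7. Nor do the documents support calling this a flaw in a formal inter-ethnic safety comparison, because none is planned.

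Confidence is high on the SAP wording. Whether the outputs themselves lack a common window depends on the OPS.

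**What to change.** In SAP 4.5:
- Keep the whole-study tables, so that no event is lost.
- Add AE and SAE incidence and worst-case laboratory, vital-sign and QTc tables by cohort and treatment, cut at a common window counted from each participant's own dose. Day 57 matches PK and TE. The last visit required of all cohorts would also serve and would keep more of the shared follow-up.
- Show follow-up duration by cohort beside the whole-study tables.
- State whether the Day 57 definition in protocol 1.1 covers the primary safety endpoints.

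Whole-study AE rates per participant-time would not replace the common window. If all AEs fell by Day 57, the same events would give a Caucasian rate of 112/154 = 0.73 to 112/196 = 0.57 times the Chinese or Japanese rate, from follow-up alone (assumed end days as above).

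Cost: SAP wording, a date filter and a few more tables to produce and read. No new data and no change to conduct. If the OPS already lists such tables, stating the window in the SAP is enough for that part.
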